## **7.7 EXTENT OF EXPOSURE**

Extent of exposure to active study medication will be calculated as the difference between the date of last intake of study drug (or respectively date of death) and the first administration of study drug + 1 day (i.e. including off-treatment periods) per patient.

The end of time in study is defined as the latest date as of the date of last documented study visit (defined in [Section 6.8.3](#)) and the date of vital status (if alive)/ date last known to be alive (if LTFU)/ date of death (if died). The time in study is the difference between the end of time in study and the date of randomisation.

A descriptive statistics table of the treatment exposure and time in study will be provided. This table will also include the total exposure/time in study summed over all patients within each treatment group and transformed to patient years as obtained by:

$$\text{Patient years} = \frac{\sum (\text{individual patient total exposure/time in study in days})}{365.25 \text{ days}}$$

In addition, the table will include the sum of exposure/time in study without/prior to rescue medication [years] and the sum from first intake of rescue medication [years] per treatment group.

A frequency table of number and percentage of patients with exposure/time in study for specific time periods will be provided by treatment group.

A Kaplan-Meier plot will be provided for exposure time and time in study.

## **7.8 SAFETY ANALYSIS**

Safety analyses of adverse events and laboratory data will be performed on the treated set.

### **7.8.1 Adverse events**

AEs will be coded using the most recent version of the Medical Dictionary for Regulatory Activities (MedDRA) coding dictionary.

The analyses of adverse events will be descriptive in nature. All analyses of AEs will be based on the number of patients with AEs (not the number of AEs). For this purpose, AE data will be combined in a 2-step procedure into AE records.

In a first step, AE occurrences, i.e. AE entries on the eCRF, will be collapsed into AE episodes provided that all of the following applies:

- The same MedDRA lowest level term was reported for the occurrences
- The occurrences were time-overlapping or time-adjacent. Time-adjacency of 2 occurrences is given if the second occurrence started on the same day or on the day after the end of the first occurrence.
- Treatment did not change between the onset of the occurrences OR treatment changed between the onset of the occurrences, but no deterioration was observed for the later occurrence

In a second step, AE episodes will be condensed into AE records provided that the episodes were reported with the same term on the respective MedDRA level and that the episodes are assigned to the same treatment. For further details on summarization of AE data, please refer to the guideline 'Handling and summarization of adverse event data for clinical trial reports and integrated summaries' [\(2\)](#).

The general AE analysis will include all adverse events (including outcome events).

For the hypoglycaemic events (reported as adverse events or separately) further evaluation is performed on episodes. The occurrences are only collapsed if they occur within  $\leq 60$  minutes of each other. The period will begin with the first hypoglycaemia onset time. If another event occurs outside this initial 60 minutes window a new period for collapsing will begin. Hypoglycaemic episodes with a missing onset time will be counted as separate episodes, regardless of other episodes on the same day.

#### 7.8.1.1 Assignment of AEs to treatments

The analysis of adverse events will be based on the concept of treatment emergent adverse events. That means that all adverse events occurring between first drug intake until 7 days after last permanent treatment stop will be considered as on-treatment (see [Table 6.7.2: 1](#)), which means, that possible treatment interruption phases of a patient will be part of the on-treatment phase.

All adverse events occurring prior to first drug intake will be assigned to ‘screening/run-in’. All adverse events occurring after last drug intake + 7 days will be assigned to treatment related ‘post-treatment’, whereby the post-treatment phase according to the previous treatment will be used (post-Lina and post-Glim respectively). Adverse events reported after the latest date as of the date of last documented study visit (defined in [Section 6.8.3](#)) and the date of vital status (if alive)/ date last known to be alive (if LTFU)/ date of death (if died)+ 1 day will be assigned to post-study. For details on the treatment definition, see [Section 6.1](#). Patients who died before last drug intake + 7 days will have their on-treatment phase assigned until the date of death.

In section 15, only adverse events assigned to on-treatment phase of linagliptin or glimepiride of the respective drug will be displayed. Further tables including also adverse events which occurred during screening/run-in and post-treatment phase will be included in Appendix 16.1.9.2 and 16.2.7.

All AEs observed during the study starting from first treatment intake will be presented in further tables.

A listing of patients with on-treatment adverse events with an onset during the non-randomised treatment will be provided.

*Further additional approaches will be implemented for the presentation of adverse events:*

- For cancer and pancreatic cancer in addition to the ‘7-day-on-treatment approach’ on the treated set, all adverse events that occurred between first study drug intake up to study end will be presented.  
There will be additional analyses including all patients who had a minimum cumulative study drug exposure of 6 months (excluding treatment gaps), using following two approaches:
  - considering all AEs starting from the date when 6 months cumulative exposure was reached up to last drug stop + 7 days
  - considering all AEs starting from date when 6 months cumulative exposure was reached up to individual day of trial completion

- For renal events, hepatic events, pancreatitis and skin reactions all adverse events that occurred between first study drug intake up until treatment stop + 30 days will be presented based on the treated set.
- For pancreatitis all adverse events that occurred between first study drug intake up until study end will be presented based on the treated set.
- Investigator reported cardiac failure will be analysed following the ‘7-day-on-treatment approach’ and also considering all events up to individual day of trial completion (refer to [Section 7.5.2.1](#)).

#### 7.8.1.2 Analysis of other significant AEs

According to ICH E3 [\(8\)](#), AEs classified as ‘other significant’ will include those non-serious adverse events with

- (i) ‘action taken = discontinuation’ or ‘action taken = reduced’, or
- (ii) marked haematological and other lab abnormalities or
- (iii) lead to significant concomitant therapy as identified by the Clinical Monitor/Investigator at a Blinded Report Planning Meeting.

#### 7.8.1.3 AE summaries

##### 7.8.1.3.1 Frequency of patients with adverse events

Frequency of patients with adverse events will be summarised by treatment, primary system organ class (SOC) and preferred term. The SOC's will be sorted according to the standard sort order specified by the European Medicines Agency (EMA), preferred terms will be sorted by frequency (within SOC). No inferential analysis is planned for routine safety comparisons.

An overall summary of patients with adverse events will be presented (including patients with any AE, severe AEs, investigator defined drug-related AEs, other significant AEs, AEs leading to discontinuation of trial drug, serious AEs).

The frequency of patients with adverse events will be summarised by treatment, primary system organ class and preferred term. Separate tables will be provided for patients with other significant adverse events according to ICH E3 [\(8\)](#), for patients with serious adverse events, for patients with drug-related adverse events, patients with adverse events leading to treatment discontinuation, patients with fatal adverse events, and by AE intensity.

An overview of adverse events from patients screened, but not treated, will be included.

### 7.8.1.3.2 Adverse event incidence rates, rate ratio and rate difference

In addition to the frequency tabulations, time-adjusted adverse event analyses will be performed for certain types of events (severe AEs, investigator defined drug-related AEs, other significant AEs, AEs leading to discontinuation of trial drug, serious AEs, and adverse events of special interest and further adverse events) by SOC and PT, respectively HLT and PT.

Therefore, the time at risk in patient years is derived as follows:

- Patients with AE:  
time at risk (AE) in days = date of start of AE with specified PT/SOC – study treatment start date + 1
- Patients without AE:  
time at risk (AE) in days = end date of time at risk – study treatment start date + 1, where end date of time at risk is the minimum of date of last study drug intake + 7 days and date of death, if applicable.  
Depending on the specific approach for how long adverse events are assigned to treatment, '+30 days' or respectively the date of trial termination may be used for the derivation of time at risk.

Total AE-specific time at risk per treatment group is then derived as:

Time at risk (AE) [years] = Sum of time at risk [days] over all patients in a treatment group / 365.25

For 'each row of a table' (e.g. displaying an SOC), time at risk is calculated using start of first AE summarized in this row; e.g. for patient with AE in a specified SOC, time at risk = date of start of AE with specified PT in a SOC – start of study treatment + 1.

The AE incidence rate per 1000 patient years can then be calculated as follows:

Incidence rate [1/1000 Patient years (pt-yrs)] = 1000 \* number of patients with AE / time at risk (AE) [years].

Further the rate ratio of the incidence rates and the rate differences with the 95% CIs will be presented for hypoglycaemia. The estimates and confidence intervals for incidence rate ratios are based on a Cochran-Mantel-Haenszel option, while estimates and confidence intervals for incidence rate differences are derived as follows:

The rate difference is defined as

$$\hat{\delta} = \frac{x}{n} - \frac{y}{m}, \text{ where}$$

x denotes the number of patients with event in treatment 1,

y denotes the number of patients with event in treatment 2,

$n$  denotes the number of patient days at risk with treatment 1 and

$m$  denotes the number of patients days at risk with in treatment 2.

The estimated variance of  $\hat{\delta}$  is defined as: 
$$\hat{\text{var}}(\hat{\delta}) = \frac{x \cdot m^2 + y \cdot n^2}{(nm)^2}.$$

Assuming normal distribution of  $\hat{\delta}$ , an approximate 95% confidence interval is given as follows, where  $z_{0,975}$  is the 97.5% quantile of the standard normal distribution:

$$CI = [\hat{\delta} \pm z_{0,975} \cdot \sqrt{\hat{\text{var}}(\hat{\delta})}]$$

#### 7.8.1.4 AEs of special interest (AESI)

Analysis of protocol specified AEs (=events of special interest)

According to the CTP the following events are considered as adverse events of special interest (AESI):

- Hypersensitivity reactions such as angioedema, angioedema-like events, and Anaphylaxis (defined by narrow SMQ 20000214 ‘hypersensitivity’)
- Skin lesions (defined by narrow SMQ 20000020 ‘severe cutaneous adverse reactions’)
- Hepatic events (defined by narrow sub-SMQ 20000010 ‘hepatitis, non-infectious’, narrow sub-SMQ 20000013 ‘hepatic failure, fibrosis and cirrhosis and other liver damage-related conditions’, narrow sub-SMQ 20000008 ‘liver related investigations, signs and symptoms’, narrow sub-SMQ 20000009 ‘cholestasis and jaundice of hepatic origin’)
- Renal adverse events (defined by narrow SMQ 20000003 ‘acute renal failure’)
- Pancreatitis (defined by narrow SMQ 20000022 ‘acute pancreatitis’ and PT ‘Pancreatitis chronic’)

Patients with these AESIs will be tabulated by treatment group.

Further, patients with pancreatic cancer (defined based on narrow BICMQ) will be tabulated by treatment group.

For all AESIs, in addition frequency tables for serious adverse events (except for pancreatic cancer as these events are on the always-SAE list), adverse events leading to discontinuation from trial drug, drug related adverse events and adverse events by severity and outcome will be presented.

The most recent version of the definitions of these AESIs according to the respective most recent MedDRA version will be used. These will be stored in the PDMAP.

#### 7.8.1.5 Events qualifying for external adjudication by the Clinical Event Committee (CEC)

Tabulations with frequency of patients with adverse events triggering CEC adjudication (based on specified SMQs according to CEC charter and manually identified) will be provided by treatment/overall, primary SOC and preferred term ~~and result of adjudication~~. Further, outcome events captured by the investigators will be contrasted with those defined by the adjudication committee.

All by adjudication confirmed events will be summarised.

For cardio- and cerebrovascular events the components as listed in [Section 5.3.1](#) as well as the types of CV deaths, the types of non-fatal MIs, types of strokes, stent thrombosis and all not assessable cases will be presented.

#### 7.8.1.6 Analysis of hypoglycaemic events

All symptomatic hypoglycaemic events, all asymptomatic events with glucose levels less than 3.0 mmol/L (or less than 54 mg/dL) and all asymptomatic hypoglycaemic events that are considered as adverse events by the investigator have to be recorded as an adverse event with additional information to assess the intensity of the hypoglycaemic event.

For asymptomatic hypoglycaemia with a measured plasma glucose concentration  $\geq 3.0$  and  $\leq 3.9$  mmol/L ( $\geq 54$  and  $\leq 70$  mg/dL), if not considered as adverse event, the plasma glucose levels values will be recorded in the CRF.

Analyses on hypoglycaemic events will be performed on the TS.

Different tables will be shown for (i) patients with investigator defined asymptomatic or symptomatic hypoglycaemia reported on the CRF, and (ii) patients with (by the investigator) confirmed hypoglycaemic adverse events and (iii) asymptomatic hypoglycaemia.

The number of patients with investigator defined hypoglycaemia (adverse events) will be tabulated by treatment group. In addition, the number of patients with different characteristics of hypoglycaemic events, including severity, symptoms, glucose level, minimum glucose level of the worst episode, number of episodes per patient as well as time to first hypoglycaemic episode will be presented.

The number of patients with hypoglycaemic events and investigator defined hypoglycaemia adverse events will be shown by age group and by use of rescue medication (yes, no).

Time to the onset of the first hypoglycaemia and first hypoglycaemia adverse event will be analysed by Kaplan-Meier estimates. A log rank test will be performed. For the details on censoring refer to [Section 6.8](#) and [7.8.1.3.2](#).

#### 7.8.1.7 Further adverse events

Patients with the following adverse events will be tabulated by treatment group: Malignancies (defined by broad BICMQ 'Malignancy'), Immunological reaction (only on SOC level, 'Immune System Disorder'). Analysis regarding malignancies as defined by broad BICMQ 'Malignancy' will be presented separately by narrow SMQ 'Malignant tumours' and SMQ 'Tumours of unspecified malignancy' and overall.

In addition, frequency tables will be provided for the following 'AE-concepts':

- angioedema (defined by narrow SMQ 20000024 'angioedema')
- arthralgia (defined by HLT 'Joint disorders') (by HLT and PT)
- bullous conditions (by HLT 'bullous condition' and PT)

For all these 'AE concepts' in addition frequency tables for serious adverse events (except for cancer as these events are on the always-SAE list), adverse events leading to discontinuation from trial drug, drug related adverse events and adverse events by severity and outcome will be presented.

The most recent version of the definitions of these AEs according to the respective most recent MedDRA version will be used. These will be stored in the PDMAP.

#### 7.8.1.8 Events qualifying for external adjudication by the Clinical Event Committee (CEC) for pancreatic events

A separate independent, blinded, external committee regularly reviews events suspected of acute pancreatitis, chronic pancreatitis, asymptomatic pancreatic hyperenzymemia and pancreatic malignancy and will evaluate whether pre-specified criteria for these adjudication events are met. Details on composition of the CEC, responsibilities and clinical event definitions are provided in the corresponding CEC charter.

Based on the CEC adjudication results, the number of patients for each of the following events will be summarized in frequency tables (overall and by adjudication trigger i.e. lab or AE):

- Acute pancreatitis (with organ failure)
- Acute pancreatitis (without organ failure)
- Chronic pancreatitis (with organ failure)
- Asymptomatic pancreatic hyperenzymemia
- Pancreatic malignancy

The analysis will be performed on TS considering the individual day of trial completion and 'on-treatment + 7 days'.

For CEC confirmed adjudicated acute pancreatitis a Kaplan Meier curve for time to first event will be presented along with a Hazard ratio and 95% CI from Cox regression based on all events up to individual day of trial completion.

#### 7.8.1.9 Events qualifying for external assessment by the Oncologic Assessment Committee (oncAC)

A separate independent, blinded, external committee regularly reviews all events suspect of solid cancer and assesses whether the cancer case is drug related or not. Details on composition of the oncAC, responsibilities and clinical event definitions are provided in the corresponding oncAC charter.

Frequency tables summarizing the relatedness will be provided.  
In addition possibly related, not related and not assessable events will be presented.

A frequency table will be provided for trigger events that cannot be confirmed as a solid tumour malignancy as defined in the charter.

The analysis will be performed on all events up to individual day of trial completion.

#### **7.8.2 Laboratory data**

The analyses of laboratory data will be descriptive in nature and will be based on BI standards. The process of standardisation and normalisation as well as standard analyses for safety laboratory data are described in the BI guidance for the Display and Analysis of Laboratory Data: (see DM&SM: Display and Analysis of Laboratory Data)(4).

Laboratory measurements will be assigned to trial phases screening/run-in, treatment period of Linagliptin or Glimepiride and post-treatment Linagliptin, post-treatment Glimepiridie, post-study period as described in [Section 6.1.1](#) and [6.7](#).

Laboratory measurements will be analysed with an on-treatment approach. Further analyses will be provided summarizing on-treatment and post-treatment measurements per treatment group.

Baseline for safety laboratory parameters will be the last available measurement before the start of randomised study drug. The last measurement taken between the first intake of randomised trial drug and seven days after the last administration of trial drug will be analysed as the last value on-treatment. In case of repeated measurements per visit, the worst value will be used.

Only patients with at least one available baseline and on-treatment value will be included in the analysis of an individual laboratory parameter.

Descriptive statistics of continuous laboratory data for safety purposes will be based on normalised values.

Laboratory values will be compared to their reference ranges (and multiples of their reference ranges) and frequency tables will be provided for the number of patients within and outside the reference range at baseline, over time and the last measurement on treatment (continuous parameters). Descriptive statistics for changes from baseline will be provided by treatment group for baseline, over time, the minimum and maximum post baseline and last measurement on-treatment for continuous parameters.

Categorical laboratory data will be presented in frequency tables for baseline, over time and last value on treatment.

Further frequency tables will summarise the number of patients with possible clinically significant abnormalities.

Details on patients with potential Hy's law cases will be listed. For the summaries on patients with elevated liver enzymes see below. A summary will also be created representing the number of patients per treatment group who experienced a doubling in creatinine on treatment compared to baseline.

A shift table from baseline, over time and last value on treatment for eGFR (MDRD) and UACR will be provided.

For these analyses the continuous diabetes related endpoints will be included in the safety analyses with respect to the reference range and in the analysis of possible clinically significant abnormalities, as far as reference ranges and thresholds for potential clinical significance exist.

#### *Specific considerations for hepatic parameters*

To support analyses of liver related adverse drug effects potential Hy's law cases are defined by the combination of the following events within one sample:

- any on-treatment value of ALT or AST (or both)  $\geq 3$  times upper limit of normal (ULN) with
- total bilirubin  $\geq 2 \times$  ULN and
- alkaline phosphatase  $\leq 2 \times$  ULN.

Further, it will be investigated if the above events occurred within a time span of 30 days. The start of the 30 day time span is triggered by each liver enzyme elevation above the defined thresholds.

Patients who fulfil one or two of the criteria for ALT/AST or total bilirubin elevations above and have no information available for the remaining parameter(s) at the same timepoint or within the 30 day time windows will be presented as well.

All calculations for the grading will be based on the originally measured laboratory values and the ULNs given by the laboratory, not on normalised values with BI standard reference ranges.

In addition ALT/AST will be used to investigate elevated liver enzymes:

- ALT/AST  $\geq 3$  x ULN
- ALT/AST  $\geq 5$  x ULN
- ALT/AST  $\geq 10$  x ULN

Frequency tables of patients with elevated liver enzymes defined by ALT and/or AST, total bilirubin and AP combinations will be provided. A scatter plot of peak ALT against peak total bilirubin will be presented with reference lines for 3 x ULN ALT and 2 x ULN total bilirubin, including an indicator for treatment received.

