### 10.6.2 Procedures

Repeat the following lab tests: ALT, AST, total bilirubin (with differentiation of bilirubin in direct and indirect) and additionally alkaline phosphates (ALP), CK (CK-MB, if CK is elevated), amylase, lipase, INR - within 48 to 72 hours and provide additional blood sample to the central laboratory for automatic reflex testing of the below listed laboratory parameters. Only in case whereby the central laboratory is not immediately available (e.g. if the logistics are such that the patient's repeat specimen would not reach the central laboratory in a reasonable timeframe), ALT, AST, total bilirubin (with differentiation of bilirubin in direct and indirect) and additionally alkaline phosphates (ALP), CK (CK-MB, if CK is elevated), amylase, lipase, INR will be evaluated by local laboratory and results are made available to the investigator

Proprietary confidential information.

© 2019 Boehringer Ingelheim International GmbH or one or more of its affiliated companies. All rights reserved.

This document may not - in full or in part - be passed on, reproduced, published or otherwise used without prior written permission.

and to BI as soon as possible. If in such a case ALT and/or AST  $\geq$  3 fold ULN combined with an elevation of total bilirubin  $\geq$  2 fold ULN are confirmed, results of the laboratory parameters described below must be made available to the investigator and to BI as soon as possible.

In addition,

- initiate close observation of subjects by repeat testing of ALT, AST, alkaline phosphates (ALP), CK (CK-MB, if CK is elevated), total bilirubin (with differentiation of bilirubin in direct and indirect), amylase, lipase, INR with repeated testing of these parameters at least weekly until ALT and or AST abnormalities stabilize or return to normal, then according to the protocol. Depending on further laboratory changes, additional parameters identified e.g. by reflex testing will be followed up based on medical judgement and Good Clinical Practices (GCP).
- initiate examination for alternative reasons for elevation of liver parameters:
  - o obtain a detailed history of current symptoms and concurrent diagnoses and medical history according to the “DILI checklist” provided in the ISF

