### 10.6.3 Decision to Stop Drug Administration

Based on the potential risk for a patient, it can be necessary to discontinue study drug treatment. This decision should be made in close cooperation between the investigator and Boehringer Ingelheim.

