### **6.7.2 Time windows for assignment to on-treatment phase**

Measurements taken prior to the first intake of randomised study drug will be considered pre-treatment values.

The date and clock time of the first drug administration will be used to separate pre-treatment from on-treatment values. Measurements taken after the first intake of randomised study drug will be considered on-treatment values if they have been obtained up to the end of the parameter-specific follow-up period as defined in [Table 6.7.2: 1](#): they will be assigned to the randomised study drug for analyses.

Measurements taken after the end of the follow-up period will be considered post-treatment values.

Table 6.7.2: 1 Endpoint specific follow-up time for assignment to active treatment

Endpoint	Last day of assignment to treatment (days after study drug stop date)
HbA1c	7
FPG	1
Body weight	7
Adverse events	7
Asymptomatic hypoglycaemia, that is not considered as adverse events	7
Laboratory measurements including eGFR and UACR	7
Vital signs	7
Waist circumference	7

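### The liver laboratory searches accept an ALT/AST elevation only to 7 days after last dose, although hepatic adverse events are also presented to 30 days

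*SAP*

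**What the plan says.** **Liver searches (SAP 7.8.2, hepatic parameters).** A potential Hy's law case needs, in one sample, "any on-treatment value of ALT or AST (or both" at 3 x ULN or more, total bilirubin at 2 x ULN or more, and alkaline phosphatase (ALP) at no more than 2 x ULN. Only the ALT/AST criterion carries the on-treatment label. A second search combines the criteria across samples within 30 days, counted from each enzyme elevation. The same block plans tables of ALT/AST at 3, 5 and 10 x ULN and a plot of peak ALT against peak bilirubin. None of these states a window.

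**General laboratory rule (SAP 7.8.2 and 6.7.2).** "Laboratory measurements will be analysed with an on-treatment approach". The last on-treatment value is "The last measurement taken between the first intake of randomised trial drug and seven days after the last administration of trial drug", and Table 6.7.2: 1 gives 7 days for "Laboratory measurements including eGFR and UACR". SAP 7.8.2 also promises further summaries of on-treatment plus post-treatment measurements, without naming the hepatic tables.

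**Hepatic adverse events (SAP 7.8.1.1).** Beside the standard 7-day approach, hepatic events are presented using "all adverse events that occurred between first study drug intake up until treatment stop + 30 days".

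**Data after stop.** The protocol flow chart marks safety laboratory tests at the follow-up visit, 30 days after the end-of-treatment (EOT) visit with a window of +7 days. SAP 6.7.3 labels anything from +8 to +44 days after last intake as a follow-up measurement. After a liver alert, Protocol 10.6.2 asks for "repeated testing of these parameters at least weekly until ALT and or AST abnormalities stabilize or return to normal", and Protocol 10.6.3 notes that "it can be necessary to discontinue study drug treatment".

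**The concern.** The laboratory search exists to find possible drug-induced liver injury whether or not anyone reported an event. As written, its starting point closes on day +7. The one laboratory sample that the protocol schedules after treatment comes about three weeks later and cannot start a search. The adverse event side of the same safety question is also shown to day +30, so a late enzyme rise can lie inside one window and outside the other.

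A second point is that the SAP leaves room for two readings of the 30-day span. If the drug is stopped after an enzyme rise, whether a bilirubin value after day +7 can complete the case depends on the reading chosen. Potential Hy's law cases are listed individually, so the choice should be fixed before unblinding.

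**Working it through.** The plan gives no figure to reproduce, and no power, event count or alpha is involved. The check compares windows, in days after last dose (last dose = day 0).

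**Inputs.** Laboratory on-treatment limit +7 (SAP Table 6.7.2: 1 and 7.8.2). Additional hepatic adverse event limit +30 (SAP 7.8.1.1). Hy's law span 30 days from each elevation (SAP 7.8.2). Follow-up visit at +30 to +37 (protocol flow chart), assuming that the EOT visit falls on the day of last dose. SAP follow-up window +8 to +44 (SAP 6.7.3).

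**1. Laboratory trigger against adverse event window.** 30 - 7 = 23 days, namely +8 to +30. An enzyme elevation first measured there lies in the hepatic adverse event window but cannot start a Hy's law search.

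**2. Follow-up sample.** Its earliest planned day is +30, which is beyond +7, so on schedule it never qualifies as a trigger. All of +30 to +37 lies inside the SAP's +8 to +44 window, with 44 - 37 = 7 days to spare if the EOT visit comes after the last dose. ALT, AST and total bilirubin are taken together at every assessment except Visit 1a (Protocol 5.2.3.2).

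**3. The 30-day span under two readings.** Let t be the day of an on-treatment elevation. If only ALT/AST must be on-treatment, the span ends at t + 30. If every component must be, it ends at min(t + 30, 7), and max(0, t + 23) days are lost.

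| t | End, ALT/AST only restricted | End, all restricted | Days lost |
|---|---|---|---|
| -23 | +7 | +7 | 0 |
| -10 | +20 | +7 | 13 |
| 0 | +30 | +7 | 23 |
| +7 | +37 | +7 | 30 |

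The literal text supports the first reading: the label sits on ALT/AST alone, and the span has its own length with no stated cut at +7. The second reading needs the general rule of 7.8.2 to override that. Under both, an elevation first measured after +7 cannot be a trigger.

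**4. Other laboratory analyses in SAP 7.8.2.** The eGFR and UACR shift tables are planned both treatment-emergent and regardless of treatment. Amylase and lipase include a follow-up value. Where later values are wanted, the SAP says so; the hepatic block has no such wording.

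**The case against.** The strongest defence is that 7 days is the pre-specified window. Protocol 7.3.3 assigns laboratory values to treatment up to seven days after last intake, the residual effect period is 7 days (Protocol 5.2.2.2), and the standard adverse event window is also 7 days. The +30 presentation is an addition, so the standard windows agree. This stands, and it is why the 7-day version should stay.

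Late injury also has other routes into the report: the general post-treatment laboratory summaries; the hepatic adverse event search to +30, whose definition includes liver-related investigations (SAP 7.8.1.4); and reporting of potential Hy's law cases on the SAE form within 24 hours (Protocol 5.2.2.2). These limit the consequence. They do not alter the case definition, and the adverse event routes depend on someone reporting the event.

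The listing of patients who meet some criteria but lack the others helps only when values are missing. A patient whose bilirubin was measured and normal at the index sample may not appear there.

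The yield may be small. Routine laboratory sampling is not required after premature discontinuation (flow chart footnote N), and follow-up may be by phone for completers without abnormalities at EOT (Protocol 3.1). Both points stand. Still, the phone option does not cover patients who stopped early, and the repeats after a liver alert can produce later values.

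**Conclusion.** The point holds for the trigger. An ALT/AST elevation first measured after last dose + 7 days is outside the potential Hy's law search and, by the general rule, outside the ULN-multiple tables and the scatter plot. The difference from the additional hepatic adverse event window is 23 days, and the scheduled follow-up sample falls wholly beyond the laboratory limit. The limit on the tables and plot is inferred from the general rule, because they state none.

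A reader might go further and infer that a case completed by bilirubin after stop is lost. The documents do not support that: on the literal wording, bilirubin and ALP up to 30 days after an on-treatment elevation may count. The SAP is ambiguous here, not exclusionary. Nor can a fixed share of the span be called lost. That would require the restrictive reading, a permanent stop and an assumed stopping day, and Protocol 10.6.3 gives no timing. It would also go too far to say that late liver injury is absent from the report, given the other routes.

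This is a gap in a descriptive safety analysis, probably with few cases behind it. The primary analysis, alpha and power are untouched.

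**What to change.** In SAP 7.8.2, hepatic parameters:

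- Keep the 7-day analyses as planned.
- Add a supplementary version of the ALT/AST multiples, potential Hy's law within one sample and within 30 days, and the ALT/bilirubin plot, using all values from first dose through the SAP follow-up window (to last dose + 44 days). Stopping at +30 would reach a follow-up sample on day +30 but miss one on days +31 to +37.
- State that bilirubin and ALP within the 30-day span may be post-treatment.
- Flag cases that arose or were completed after stop.

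The cost is a few sentences of SAP text and one extra set of descriptive tables from data already collected, probably with few added cases. No new visits or samples are needed.
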